If study participation is discontinued due to safety reasons, participants will receive up to three follow-up visits, allowing adequate time for appropriate psychiatric referrals to treaters in their communities, or if present, appropriate psychiatric follow up access is assured with their treating provider. If emergent suicidality were to occur during the course of the study, the supervising clinician will then directly assess the level of risk and take the appropriate action (including contacting treatment providers, working on a safety plan, arranging for emergency evaluation via an ER, calling 9-1-1, etc.). The clinician will document the actions taken, and it will be noted in the participant's file. Subjects who discontinue due to non-compliance with the protocol will receive a referral to treaters in the area.

Follow-up visits are optional and are at no cost to participants. These visits are not part of the clinical trial and no research data will be collected during follow-up. Subjects who fail to keep study appointments, or are non-compliant may be dropped from the study. These study subjects will be given a referral to treaters in their area but will not be offered three follow-up visits.

If a subject would like us to forward their clinical history to his/her primary care physician, or a new clinician, we will forward any pertinent information with the proper completed release of information authorization form. If a subject who has come from the clinic of the investigator happens to drop out of the study, he or she will return to his or her treating physician.

Lost to Follow-Up

If a clinical staff is unable to contact a subject or if the subject fails to appear for a visit, three documented phone calls should be made, followed by a certified letter. The certified letter should detail the need for the subject to appear for a visit, the site's unsuccessful attempts to contact the subject, and that failure to contact the site will result in the subject being withdrawn from the study.

If the certified letter is returned to the site as undeliverable or the letter is delivered but the subject does not contact the site and no other contact is made with the subject or the subject's caregiver, then the subject will be considered Lost to Follow-up and discontinued from the study. All attempts to contact the subject will be documented.

STUDY ASSESSMENT SCALES AND FORMS

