- Quality of Life Enjoyment and Satisfaction Questionnaire (Q-LES-Q; (Endicott, Nee, Harrison, & Blumenthal, 1993)): a 16-item questionnaire to evaluate the degree of enjoyment and satisfaction experienced in eight areas of daily functioning.

Subject-Rated Safety Measures

(Administered at week 1, week 2, week 3, Midpoint, week 6, Endpoint, and Follow Up)

- The tPBM Self-Report Questionnaire (TSRQ) – An open-ended questionnaire focusing on potential inconveniences and discomforts related to the tPBM. It will be offered at week 3 and week 6 of the study (after at least two tPBM sessions have been delivered).

Observer-Rated Behavioral Measures

(Administered at baseline and endpoint)

- Social Responsiveness Scale-Second Edition Informant-Report (SRS-2; (Constantino & Gruber, 2012)): a 65-item rating scale completed by parents/caregivers that is used to measure the severity of autism spectrum symptoms of the subjects as they occur in natural settings.
- MGH Social-Emotional Competence Scale-Informant (MGH-SECS-I): This is a 37-item scale that assesses change in the frequency and severity of core and associated symptoms of ASD.
- Adult Behavior Checklist (ABCL; (Achenbach & Rescorla, 2003)): An observer-rated assessment of maladaptive behavioral and emotional problems, social competence and substance use in adults ages 18-50.

Data Collection Forms

Several procedures are in place to assure data integrity and protocol adherence. We will use Research Electronic Data Capture (REDCap) to support direct data entry by patients and study staff. REDCap is a free, secure, HIPAA compliant web-based application hosted by the Partners HealthCare Research Computing, Enterprise Research Infrastructure & Services (ERIS) group. REDCap is an electronic data capture system that streamlines data collection and ensures data integrity. REDCap software allows researchers to design and implement study surveys electronically for collecting, storing, retrieving, and manipulating data.

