54 subjects will be randomized (1:1) into the tPBM or placebo/sham group and be treated for 8 weeks post randomization. This design largely protects against the bias introduced by confounding factors.

We will rely on comparisons of the participants' performances in each study arm (placebo/sham and tPBM) at baseline prior to the initiation of treatment relative to their scores at the last assessment (completion/drop-visit). Since we are following subjects over a short period, missing data are not expected to impact our analyses such that standard statistical analyses will be employed. Specifically, we will employ longitudinal mixed-effects regression models (RM) with random effects for the subjects using Stata 16.0 (StataCorp, 2019). The RMs will use robust standard errors to account for the repeated measures on each subject. We will test binary data using mixed-effects logistic RMs, count data with mixed-effects Poisson RMs, and normally distributed data with mixed-effects linear RMs. Each model will predict outcome scores from treatment group (placebo/sham or tPBM), study visit (continuous predictor), and the treatment group-by-study visit interaction. All analyses will be intent to treat (ITT).

10. Monitoring and Quality Assurance

Consistent with good clinical practice, safety will be monitored at each study visit by a subject's assigned clinician. This clinician will be available 24 hours a day by page. The principal investigator will supervise all study activities including ratings and reported adverse events. All procedures have been designed to minimize subject discomfort, and no subject will be asked to engage in research procedures not outlined in the consent form.

Safety will be monitored through treatment-emergent adverse events. Subjects will be monitored for adverse events at each visit. All adverse events will be recorded. A subject may be dropped from the study or dosage may be decreased at any time due to adverse events. All adverse events will be reported to the PHRC according to PHRC guidelines. All concomitant medications will be assessed at every study visit.

All adverse events will be recorded from the time of Informed Consent through study completion, or termination. The Adverse Event CRF must be completed and submitted to the IRB and Niraxx, as required. Regulations for adverse event handling and reporting contained in the FDA and ICH Guidelines will be adhered to.

Overview and Definitions

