The study subjects will undergo frequent clinical evaluations including depressive scores, concomitant medications, adverse events, and serious adverse events and unexpected device events will be recorded from study entry through completion. Additionally, doctors must monitor a subject's safety by asking the subjects frequently about the subject's own comfort during treatment application.

If skin erythema is present, treatment will be suspended. Patients will be instructed to contact the study site principal investigator or a member of his staff at any time between visits concerning adverse events or worsening of symptoms. If at any study visit the subjects' clinical condition is significantly worsened from baseline (operationalized as the clinical global impression improvement score, CGI-I, of 6 or higher) or if a subject becomes actively suicidal with intent and/or plan, based on the clinical interview, the subject will be offered to start an antidepressant medication. If the subject were deemed at imminent danger as a result of suicidality, s/he would be discontinued from the study and referred to appropriate clinical treatment (see 6.1.5 Study Discontinuation).

Study staff responsible for data collection and storage will be aware of and comply with all regulatory requirements related to adverse events. If a patient becomes ill or is injured as a direct result of study participation, medical care will be made available. All adverse events (and device events) will be followed to resolution and reported to the MGH IRB as serious if,

1. They are unanticipated and possibly related to the study (same reporting as SAE) or
2. They meet any one of the following criteria:
 - Any fatal event,
 - immediately life-threatening event,

- permanently or substantially disabling event,
- event requiring or prolonging inpatient hospitalization, or any congenital anomaly.
- This also includes any event that a study investigator judges to impose a significant hazard, contraindication, side effect, or precaution.

The Principal Investigator ([name]) will have weekly meetings with study staff; during these meetings, they will discuss all Adverse Event reports to identify any safety concern. Based on such concerns they will be able to decide whether a temporary discontinuation of study enrollment, modifications of the study protocol, or to terminate the study is necessary.

Data Safety Monitoring Board

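### Visits after a safety discontinuation collect no research data, although the protocol asks for the resolution and outcome of adverse events, so the later course of events open at exit may go unrecorded

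*Combined protocol and SAP*

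**What the plan says.** **Places that end data collection at exit**

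- Section 6, Study Discontinuation: "If study participation is discontinued due to safety reasons, participants will receive up to three follow-up visits". Then: "Follow-up visits are optional and are at no cost to participants". Then: "These visits are not part of the clinical trial and no research data will be collected during follow-up". Subjects dropped for missed appointments or non-compliance "will not be offered three follow-up visits".
- Section 10, opening text: "All adverse events will be recorded from the time of Informed Consent through study completion, or termination".
- Section 6, Study Assessment Scales and Forms: the CTAE is scheduled at baseline, at treatment visits and at the final visit, and nowhere later.
- Appendix B, Table II: the last column is Week 8 (endpoint or early termination). There is no follow-up column.

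**Places that need information from after exit**

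- Section 10, Safety Monitoring: "All adverse events (and device events) will be followed to resolution and reported to the MGH IRB as serious if", followed by a list of criteria.
- Section 10, Reporting Procedures for All Adverse Events: every adverse event must be given, among other attributes, a resolution date (where applicable) and an outcome.
- Section 6, Study Assessment Scales and Forms: the CTAE is described as recording duration and outcome, among other things. The heading over the tPBM Self-Report Questionnaire (TSRQ) reads "Administered at week 1, week 2, week 3, Midpoint, week 6, Endpoint, and Follow Up", while the text beneath it names weeks 3 and 6 only.

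**The exit visit.** Study Discontinuation asks subjects who leave early to do the final-visit tasks when they stop. Section 7, Withdrawal from the Study, lists those tasks, which include the CTAE, the TSRQ, concomitant medications and examination of the exposure sites, and qualifies them as to be done if feasible.

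**The concern.** A subject removed because of an adverse event may still have that event on the exit day. The plan then offers up to three visits but excludes them from data collection, while other sections ask for the event's resolution and outcome. A site that follows the Study Discontinuation text closely could leave the event open on the CRF, even though the study offers further visits at which its course could be seen.

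Safety is part of Primary Aim 1, and the Data Analysis section lists safety and tolerability among the secondary outcomes. How events end matters to that assessment. The Background section itself reports, as part of the tolerability account of the open-label pilot, that both subjects with events recovered. Here the same information could be missing for events that ended a subject's participation.

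**Working it through.** No arithmetic applies. The check is to follow one subject whose participation ends for safety with an event still open, and to ask at each step what the protocol lets the site record.

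1. **Exit day.** If the exit visit is feasible, the CTAE and TSRQ are completed. Occurrence, seriousness, intensity, relationship and action taken are on record up to that day.

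2. **After exit: is the CTAE covered by the ban on research data?** The Data Analysis section names the CTAE and the TSRQ as the measures of safety and tolerability. They are therefore study outcome measures, and the exclusion in Study Discontinuation reaches them.

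3. **Does another section reopen recording?** No. The recording window in Section 10, the CTAE schedule in Section 6 and Table II all stop at termination or the final visit. Together with Study Discontinuation, four places give the same cut-off.

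4. **What is still required for this event?**
   - The Safety Monitoring sentence asks for follow-up to resolution, but it ends in a conditional. It can be read as covering all events, or only those meeting the criteria listed after it.
   - Reporting Procedures is not limited in that way. It covers all adverse events during the study and requires an outcome for each, and a resolution date where one applies.
   - The CTAE's own description includes duration and outcome. Neither can be final for an event that is still open.
   
   The second and third requirements carry the point without the first.

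5. **Is the status of follow-up visits consistent?** No. Study Discontinuation opens by encouraging subjects who stop tPBM to stay enrolled by means of follow-up visits, which treats such visits as part of the study. Later, under the same heading, follow-up visits are placed outside the trial.

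6. **Does the missing period bear on causality grading?** In part. Section 10 makes abatement once treatment stops one criterion for a definite relationship to the device. Abatement is seen only after stopping, which for this subject is after recording has ended. The definite grade also needs reappearance on repeat exposure, so this is not the only obstacle to assigning it.

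7. **Who is affected?** Subjects whose participation ends, with an event open at exit. Those who stop only the treatment and stay enrolled continue to have study visits. Subjects dropped for non-compliance are offered no follow-up visits, and no section says how an open event would be completed for them.

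8. **The TSRQ.** Its heading lists a follow-up administration. The text under it gives weeks 3 and 6, and Table II gives weeks 1, 2, 3, 4, 6 and 8 with nothing later. The three do not agree, but the follow-up entry appears in the heading alone and may be a stray word. This is the weaker part of the conflict.

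**The case against.** The strongest reply is that the sections can be harmonised. The ban applies to optional visits meant for arranging psychiatric care. Safety follow-up need not happen at those visits. The Section 10 window can be read as the period in which new events are captured, which would not prevent the outcome of an event already logged from being completed. Section 10 also provides for medical supervision until symptoms resolve after an adverse-event withdrawal, and for detailed follow-up information on request.

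That reading is possible, so it cannot be said that a site is unable to comply. But it leaves no study visit, schedule entry or form window to carry the outcome, and the site has to infer that recording continues when four places indicate that it stops.

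Other parts of the reply stand in full and limit the point:

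- **A reader might infer that safety data are cut off for the subjects who were harmed.** The exit visit contradicts this. Only the course after exit is at risk.
- **A reader might infer bias in favour of the device.** The documents do not show it. Occurrence is captured whatever happens at follow-up, Section 9 plans no between-arm comparison of event duration or resolution, and nothing states that open events will be more frequent on active treatment.
- **A reader might infer that the DSMB would see serious events without outcomes.** That could apply only to serious events still open at exit. The DSMB receives unblinded data, and its chair is told of every serious event.

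**Conclusion.** The point holds as an internal conflict over data recording. For events open when participation ends, the protocol asks for resolution and outcome but assigns no study visit or form to collect them, and it states that the visits on offer collect no research data. What may be lost is the later course, resolution date and final outcome of those events.

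The size cannot be expressed as a percentage. The documents give no rate of safety discontinuation and no rate of events open at exit. The denominator is itself unsettled: Section 6 randomizes up to 27 subjects 1:1 (13 or 14 per arm) and Section 9 randomizes 54 (27 per arm). Any share of an arm would rest on an invented count.

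The conclusion assumes that CTAE entries count as research data, which follows from their listing as an outcome measure, and that the exit visit takes place. Where it is not feasible, more than the later course could be missing. The change is worth making because it replaces an explicit rule at little cost. It takes no view on clinical management.

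**What to change.** Reconcile Study Discontinuation and the CTAE description in Section 6, the recording window, Safety Monitoring and Reporting Procedures in Section 10, and Table II:

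- **Study Discontinuation:** say that no efficacy data are collected at follow-up visits, but that the CTAE is updated for any adverse event open at exit until it resolves or the visits end. Separate these visits from those of subjects who stop tPBM and remain enrolled.
- **Section 10 recording window:** extend it for events open at termination, and settle which events the Safety Monitoring sentence covers.
- **CTAE schedule and Table II:** add a follow-up entry for the CTAE.
- **Subjects dropped for non-compliance with an open event:** attempt to obtain the outcome by phone or REDCap where consent and contact permit. Some will be unreachable.
- **TSRQ:** make its heading, its item text and Table II agree. Repeating it after treatment has stopped is optional.

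The cost is protocol and consent wording plus a little participant and staff time. The form already exists and the visits are already offered.

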Primary outcome measure of efficacy will be reduction in ASD symptoms as measured by change from baseline on the clinician-rated SRS-2. Responders will be defined as those who demonstrate a $\geq 25\%$ reduction in SRS-2 total score *and* a score of 2 or 1 on the CGI-ASD-Improvement subscale ("much" or "very much improved").

Secondary outcome measure:

1. Treatment-related changes in associated psychopathology, social cognition, executive functions will be assessed by:
 - MGH Social-Emotional Competence Scale (MGH-SEC Scale; clinician- & observer-rated)

- Social Responsiveness Scale-Second Edition (SRS-2; self- & observer-rated)
- Adult Behavior Checklist (ABCL; self- & observer-rated)
- Behavior Rating Inventory of Executive Function-Adult Self Report Version (BRIEF-A) or parent version (BRIEF-P) for youth
- Adult ADHD Self-Report Scale (ASRS) & clinician-rated Adult ADHD Investigator Symptom Report Scale (AISRS) and CGI-ADHD scale
- Quality of Life Enjoyment and Satisfaction Questionnaire (Q-LES-Q)
- Hamilton Anxiety scale (HAM-A) & clinician-rated CGI-Anxiety scale
- Hamilton Depression scale (HAM-D) & clinician-rated CGI-Depression scale

2. Safety and tolerability will be assessed by:

- The monitoring of spontaneous treatment-emergent adverse events with the Clinician-rated Treatment-emergent Adverse Events Log (CTAE)
- tPBM Self-Report Questionnaire (TSRQ)

SAFETY

Consistent with good clinical practice, safety will be monitored at each study visit by a subject's assigned clinician. This clinician will be available 24 hours a day by page. The principal investigator will supervise all study activities including ratings and reported adverse events. All procedures have been designed to minimize subject discomfort, and no subject will be asked to engage in research procedures not outlined in the consent form.

If study participation is discontinued due to safety reasons, participants will receive three follow-up visits, giving adequate time for appropriate psychiatric care to be arranged.

Study Treatment

Safety will be monitored through treatment-emergent adverse events and subject rated TSRQ responses. Subjects will be monitored for adverse events at each visit. All adverse events will be recorded. A subject may be dropped from the study or dosage may be decreased at any time due to adverse events. All adverse events will be reported to the PHRC according to PHRC guidelines. All concomitant medications will be assessed at every study visit.

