Based on human clinical trial experience to date and sale of the device for its intended use of treating periorbital wrinkles since March 2008, each adverse event listed below has been reported by less than 0.1% of all subjects and users:

- Application Site Erythema
- Application Site Pain
- Application Site Discomfort
- Application Site Warmth
- Application Site Reaction
- Headache

Additional information on adverse events and prior clinical experience can be found in the User Guide. Other potential risks are described below:

- Risk of Depression, Suicidality & Manic Switch: Worsening of depression and increased suicidality are possible complications of antidepressant treatments which could be prescribed to subjects with ASD and mood disorders. We will minimize this risk by selecting only subjects who do not present active suicidal ideation at screening. We will also discontinue any subject who develops active suicidal ideation during the course of the study and arrange for appropriate levels of care and standard treatment. Manic switches are possible adverse events and will be closely monitored during treatment as well. Regularly scheduled clinical study visits will allow early recognition of treatment-emergent suicidal ideation or prodromal hypomanic signs. Subjects who develop mania or hypomania will be discontinued and provided appropriate level of care.

Risks of Assessments/Questionnaires

Answering detailed questionnaires may create a mild degree of inconvenience for the subjects and will be monitored by study clinician. Some questions may make subjects feel uncomfortable because of the nature of the question topics. Some questions ask about possibly sensitive information, including questions pertaining to alcohol and drug abuse. Subjects may refuse to respond to any questions they do not feel comfortable answering.

Adverse events and unanticipated problems will be reported to the PHRC according to current guidelines. We will follow and adhere to all guidelines as defined and outlined on the Partners Human Research Committee web site: http://healthcare.partners.org/phsirb/adverse_events.htm

Other Adverse Events Related to Study Treatment

Problems and side effects not listed above and not known at this time could occur. Subjects will be informed of any newly discovered risks as investigators come to learn of such knowledge, if applicable.

Subject Disposition Criteria

Withdrawal from the Study

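### Depressive scores are collected for safety, but individual worsening on HAM-D or CGI-I is not tabulated by arm, so the safety reporting is incomplete

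*Combined protocol and SAP*

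**What the plan says.** - **Section 10, Safety Monitoring:** "The study subjects will undergo frequent clinical evaluations including depressive scores". The same paragraphs define significant worsening from baseline as a CGI-I of 6 or higher, and use it only to trigger clinical action.
- **DATA ANALYSIS, Secondary outcome measure, item 1** (associated psychopathology, social cognition, executive function) contains "Hamilton Depression scale (HAM-D) & clinician-rated CGI-Depression scale".
- **Item 2** (safety and tolerability) has two entries: the CTAE log of spontaneous treatment-emergent events, and the TSRQ, described in the scales section as "An open-ended questionnaire focusing on potential inconveniences and discomforts related to the tPBM".
- **Section 9** assigns "normally distributed data with mixed-effects linear RMs" and gives every model the same three terms: group, visit as a continuous predictor, and their interaction.
- **Appendix B, Table II** schedules HAM-D at Weeks 0, 4 and 8 and the CGIs at every visit.
- **Section 7** lists this among other potential risks: "Worsening of depression and increased suicidality are possible complications of antidepressant treatments which could be prescribed to subjects with ASD and mood disorders".
- **Section 2** makes efficacy and safety together the primary aim.

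**The concern.** The plan does classify individuals in one direction. The primary outcome defines a responder by a reduction of at least 25% in SRS-2 together with a CGI-ASD improvement score of 1 or 2. There is no counterpart for getting worse, although Safety Monitoring already supplies a CGI-I level for it. A depression score that is gathered partly for safety thus reaches the results only through a model of group trajectories, and such a model can show no difference while a minority deteriorates. At stake is how much weight the safety half of the primary aim can bear. A statement that tPBM raised no psychiatric concern would rest on what clinicians happened to log, with no systematic count from the ratings made on every subject.

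**Working it through.** The documents state no HAM-D mean, SD, threshold, worsening rate, alpha or power, so there is no figure of the plan's own to reproduce. All point changes, SDs and rates below are assumptions. Both stated sample sizes are used: up to 27 randomised (section 6, 13-14 per arm) and 54 randomised (section 9, 27 per arm).

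**1. Following each score to the results.**

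| Data | Collected | Safety role stated | By-arm safety analysis |
|---|---|---|---|
| HAM-D | Weeks 0, 4, 8 | Depressive scores, section 10 | None |
| CGI-I | Every visit | 6 or higher = worsening, section 10 | None |
| CTAE | Week 0 onward | Item 2 | Listed as a safety outcome |
| TSRQ | Week 1 onward | Item 2 | Listed as a safety outcome |

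No section defines a HAM-D worsening margin, a count or shift table, or a rule for when a HAM-D rise becomes an adverse event.

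**2. Cancellation in a mean.** If a fraction f worsens by W and the rest improve by b, the arm mean is fW - (1-f)b. It is zero when b = fW/(1-f).
- f = 0.20, W = 1 SD: b = 0.20/0.80 = 0.25 SD.
- 2 of 13 at +8, 11 at -2: (16 - 22)/13 = -0.46 points.
- 3 of 14 at +8, 11 at -2: (24 - 22)/14 = +0.14.
- 5 of 27 at +8, 22 at -2: (40 - 44)/27 = -0.15.

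**3. Chance that the model signals it.** The last two cases were simulated as subject slopes over Weeks 0, 4 and 8 (residual SD 2.5, between-subject SD 5, sham change 0, Welch test, two-sided 5%, 5,000 runs). With 14 against 13 subjects, the mean Week 8 difference was 0.15 and 1.1% of runs were significant in either direction. With 27 against 27, it was -0.14 and 1.5%.

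No offsetting gain is needed for the signal to be weak. If 20% worsen by 1 to 2 SD and the rest do not change, the mean moves 0.2 to 0.4 SD. The difference detectable with 80% power is (1.96 + 0.84) x sqrt(2/n), which is 1.10 SD at n = 13 and 0.76 SD at n = 27.

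**4. A transient rise.** With complete data and visit coded in weeks, the slope weight at time t is (t - 4)/32, because the squared deviations of 0, 4 and 8 from 4 sum to 16 + 0 + 16 = 32. The weights are -0.125, 0 and +0.125. The Week 4 score has weight zero, so a rise seen only at Week 4 contributes nothing to the group-by-visit estimate. Under Safety Monitoring a worsened subject may be offered an antidepressant, so a rise that later resolves is a plausible pattern.

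**5. What a count can deliver.** The chance of at least one case in the active arm is 1 - (1-p)^n. At p = 0.15 this is 0.88 (n = 13), 0.90 (n = 14) and 0.99 (n = 27). With zero cases, the upper end of the exact two-sided 95% interval is 1 - 0.025^(1/n): 24.7% at n = 13 and 12.8% at n = 27. Comparing 20% with 5% between arms has power of about 0.21 at 13-14 per arm and 0.38 at 27; 80% power needs 76 per arm.

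**The case against.** The strongest reply is that the protocol already captures individual deterioration. Section 10 defines an adverse event as any unfavourable sign, symptom or disease, related or not, and requires events observed by the investigator as well as those reported by the subject to be documented. HAM-D and the CTAE are both completed by clinicians, so logging does not depend on the subject volunteering a complaint. Worsening or emergent major psychiatric disorder and emergent suicidality are withdrawal reasons, and the reason for withdrawal is recorded. The DSMB sees unblinded data, although its scheduled review is of serious events. Eligibility excludes unstable psychiatric conditions and active suicidal ideation. All of this stands. What it leaves open is the rating that rises without being judged an event: nothing links a score to the log, and the TSRQ concerns discomfort from the device.

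Two stronger readings are tempting, and the documents support neither. A reader might infer that the protocol names worsening depression as an effect of tPBM. Section 7 attributes it to antidepressants that could be prescribed. A reader might also infer that harm would go unreported. The routes above can catch clinically evident cases.

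It is also fair to say that section 9 permits logistic models and does not forbid descriptive tables, so analysis of HAM-D only as a score is an inference from the lack of any defined HAM-D category. Further, the cancelling scenarios are constructed, and the count is itself noisy. In simulations with 13 against 14 subjects, an assumed SD of 4 and a rise of 6 or more counted as worsening, the tPBM count exceeded the sham count in only about 60-78% of trials. The table therefore adds information but does not guarantee that a problem is seen.

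**Conclusion.** The point holds as incomplete safety reporting. The plan collects depressive scores and CGI-I for safety, but its safety outcome omits both, and it tabulates no individual worsening by arm. Depressive worsening that is not logged as an adverse event or withdrawal reason may not appear in the safety results.

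That conclusion comes from reading the sections together and needs no numerical assumption. The zero weight at Week 4 is exact, given complete data and visits coded in weeks. The size of any masking cannot be established from the documents; the figures above show only that masking is arithmetically easy at either stated sample size. This is an inexpensive improvement to the safety analysis, and it does not invalidate the efficacy analysis.

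**What to change.** Add to DATA ANALYSIS, Secondary outcome measure, item 2, one descriptive table by arm, with the number assessed and exact 95% intervals, giving the number and percentage of subjects with:

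- (a) any post-baseline CGI-I of 6 or 7, naming the CGI domain. The scales section describes the CGI for ADHD and ASD only, and CGI-Depression appears only in the outcome list;
- (b) a HAM-D rise from Week 0, at Week 4 or at the last assessment, of at least a margin that the sponsor fixes before unblinding;
- (c) discontinuation for suicidality, mania or hypomania.

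Keep the HAM-D mixed model as the efficacy analysis. No treatment or stopping rule changes.

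Two inconsistencies affect the table and must be reconciled. Section 6 randomises up to 27 and section 9 randomises 54, which sets the denominators. Study Discontinuation (section 6) mandates termination for active suicidality, while Safety Monitoring (section 10) describes an offer of treatment and ties discontinuation to imminent danger. Count (c) depends on which was followed; this review takes no position on the clinical rule.

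The cost is a few lines of text and one table from data already collected. The downside is imprecision: at 13-14 or even 27 per arm the counts support no between-arm test and should be presented as description only.
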